## 4 Statistical Methodology

### 4.1 Planned Analyses

The FAS will be used for summaries of baseline characteristics and background data; the Safety population will be used for all safety analyses; the PPP will be used for the primary and secondary analyses; and the Evaluable population (if required, see [Section 3.5.4](#)) will be used for supporting analysis of the primary endpoint, and all other immunogenicity endpoints.

Descriptive statistics will be used to present all safety and immunogenicity results: number of observations (n), mean, standard deviation (SD), median, minimum (min), maximum (max) for continuous data and frequency and percentage for categorical data. Ninety-five percent confidence intervals (CIs) will also be presented for some immunogenicity criteria. Geometric means and 95% CIs will be calculated by taking the anti-logs of the means and 95% CI of the log transformed immunogenicity parameters. Exact CIs based upon the binomial distribution will be calculated for percentages.

Statistics will be displayed for the following:

- Seqirus QIV
- Comparator QIV
- Overall

Summaries by age strata will be:

- 6 through 35 months
- 36 through 59 months

In the summary tables, the strains will be displayed as follows:

- A/H1N1 for *A/California/7/2009 (H1N1)pdm09-like virus*
- A/H3N2 for *A/Hong Kong/4801/2014 (H3N2)-like virus*
- B/Yamagata for *B/Phuket/3073/2013-like virus (B/Yamagata lineage)*
- B/Victoria for *B/Brisbane/60/2008-like virus (B/Victoria lineage)*

All data will be listed.

### 4.2 Interim Analysis

An interim analysis is defined as the analysis of immunogenicity and safety data collected from the active study period (Day 1 to Study Exit Visit). Details of the summaries and analyses to be performed are provided in subsequent sections, with tables and listings to be produced highlighted in [Section 5.3](#) and [Section 5.4](#).

A Data and Safety Monitoring Board (DSMB) review of safety data will be conducted after approximately one third of subjects (or a minimum of 300 subjects) in the 36 through 59 months age group have received the first vaccination and have had an opportunity to enter at least the first 7 days of safety data post-vaccination.

Recruitment in the 36 through 59 months age cohort will not be halted during the period of the data cut and DSMB review. Enrolment in the younger age cohort (subjects 6 months through 35 months of age) will only commence after the DSMB has reviewed the safety data and recommended that the study may proceed.

A second safety data cut will be performed when approximately one third of subjects (or a minimum of 300 subjects) in the 6 through to 35 months age cohort have received the first vaccination and have had an opportunity to enter at least the 7 days of safety data post-vaccination. A DSMB meeting will be convened to review and assess the available safety data. Recruitment in the 6 through 35 months age cohort will not be halted during the period of the data cut and DSMB review.

Halting rule triggers may lead to additional DSMB safety data review as defined in the DSMB Charter.

An interim CSR will be produced from data generated from Visit 1 through to the Exit Visit.

A final consolidated CSR will present all immunogenicity and safety data collected from the active study period and safety data through to the final evaluation (180 days following the last vaccination dose).

### **4.3 Disposition of Subjects**

The number of subjects screened, enrolled into the study, in each study population, who completed the study, and the reasons for any premature discontinuation from the study will be presented in summary tables by treatment group, by age strata (6 through 35 months, 36 through 59 months) and overall. The number in the full analysis set will be used as the denominator.

The number of subjects who are excluded from each of the Evaluable and Per-Protocol populations will be summarized by treatment group, by age strata (6 through 35 months, 36 through 59 months) and overall.

The primary reason for discontinuing the study product, or withdrawing a subject from the study, will be summarized by treatment group, by age strata and overall.

The number of screen failures, and reason for screen failure will also be displayed.

### **4.4 Baseline and Demographic Characteristics**

All baseline and demographic characteristics will be summarised by treatment group, age strata, and overall. This will include age, gender, race, ethnicity, weight, pre-vaccination temperature, medical history, and previous vaccination history.

Medical history will be coded according to MedDRA version 19, and will be displayed by system organ class and preferred term, using the MedDRA internationally agreed order.

For prior vaccination history, the number and percentage of subjects who have ever been vaccinated, who have been vaccinated in the 2015/2016 season, and have been assigned to receive 1 or 2 vaccinations during the study, will be summarised.

## 4.5 Exposure

The number and percentage of subjects that received vaccination, the side/site/route of each vaccination, and received vaccinations according to protocol will be summarised by treatment group, by age strata, and overall, for Visit 1 and Visit 2.

## 4.6 Concomitant Medication

Incidence of concomitant medication will be presented by treatment, age strata, therapeutic area and preferred drug name.

Concomitant medications are all medications taken during the study period, including those started before but ongoing at vaccination.

Where a medication start date is partially or fully missing, and it is unclear as to whether the medication is prior or concomitant, it will be assumed that it is concomitant.

### Note:

Medications are coded using WHO Drug dictionary version March 2016.

Prior medications will be listed only.

## 4.7 Primary and Secondary Analysis

### 4.7.1 Primary Endpoints

Serum HI antibody levels of all participants will be determined in triplicate (HI1, HI2 and HI3) on serum separated from the whole blood. Pre- and post-vaccination samples will be titrated in duplicate, simultaneously. The titer assigned to each sample shall be the geometric mean of three independent determinations i.e. Assigned titer= $\exp[(\log(\text{HI1}) + \log(\text{HI2}) + \log(\text{HI3}))/3]$

GMT and SCR will be based on the following:

- HI antibody titer for each strain: All analyses involving HI antibody titer (namely group GMT within a treatment group) will be performed on the log scale and the resultant summary statistic back-transformed to derived GMT
- Seroconversion: For each strain the subjects will be classified as 'seroconverted' if either they have a pre-vaccination HI antibody titer < 1:10 and a post-vaccination HI antibody titer  $\geq$  1:40 or a pre-vaccination HI antibody titer  $\geq$  1:10 and a  $\geq$  4-fold increase in post vaccination HI antibody titer. Otherwise they will be classified as 'not seroconverted'

## 4.7.2 Method of Analysis for Primary Outcome

### Primary Objectives

The primary objective of this study is to demonstrate that vaccination with Seqirus QIV elicits an immune response that is not inferior to that of a US-licensed comparator QIV containing the same virus strains as Seqirus QIV, among a pediatric population 6 through 59 months of age.

### Primary Endpoints

Co-primary immunogenicity endpoints of GMT and SCR for each virus strain contained in the vaccine will be assessed among a pediatric population 6 through 59 months of age.

The rate of seroconversion is defined as the percentage of subjects with either a pre-vaccination hemagglutination inhibition (HI) titer < 1:10 and a post-vaccination HI titer  $\geq$  1:40 or a pre-vaccination titer  $\geq$  1:10 and a  $\geq$  4-fold increase in post-vaccination titer.

The non-inferiority of Seqirus QIV compared to the US-licensed comparator QIV will be assessed by the 8 co-primary endpoints of GMT and SCR.

In line with the FDA Guidance on seasonal inactivated influenza vaccines (*Guidance for Industry Clinical Data Needed to Support Licensure of Seasonal Inactivated Influenza Vaccines 2007*), Seqirus QIV will be considered to be non-inferior to the US-licensed comparator QIV if, for each of the four strains, the following statistical criteria are met:

- The upper bound of the two-sided 95% confidence interval (CI) on the ratio of the GMTs does not exceed 1.5. The GMT ratio will be calculated by GMT US-licensed comparator QIV / GMT Seqirus QIV
- The upper bound of the two-sided 95% CI on the difference between the SCRs does not exceed 10%. The difference in SCRs will be calculated by (Seroconversion US-licensed comparator QIV – Seroconversion Seqirus QIV). The 95% CI will be computed based on the binomial distribution.

To determine the GMT ratio (adjusted analysis) a general linear model (GLM) will be fitted on log transformed (natural log) post-vaccination HI titer as the outcome variable and terms for covariates: vaccine treatment, pre-vaccination HI titer, age stratum, gender, vaccination history, age-by-vaccine interaction and study site. Potential covariate interaction effects will also be examined in the fit of the GLM. From the model an adjusted difference in least square means (on the log scale) will be produced with 95% confidence limits. The estimated difference and the confidence limits will be back transformed to obtain an *adjusted* GMT ratio with 95% confidence limits. Each of the four strains will be analysed separately. The adjusted GMT ratio will be the result for which the non-inferiority assessment of the HI GMT co-primary endpoint will be based on.

The complete set of covariates that will be used in the model to calculate the adjusted GMT ratio will include treatment group (2 treatments), pre-vaccination mean GMT titer (value), age strata (2 categories, 6 through 35 months or 36 through 59 months), gender (male or female), influenza vaccination received prior year (Yes or No), Number of Dose (1 vs 2), and investigator site (site identifier).

The GLM specification is:

- Adjusted Analysis GMT Model: Log-transformed Post-vaccination HI Titer = Vaccine + Age Strata + Gender + Vaccination History [y/n] + Log-transformed Pre-vaccination HI Titer + Site + Number of Dose [1/2] + Age Strata\*Vaccine.

For any strain, the interaction term *Age Strata\*Vaccine* will be removed from the fit of the model if it is assessed to be not significant.

The measure of the *unadjusted* GMT ratio based on post-vaccination GMTs only will also be presented.

The PPP will be the primary analysis population for the primary immunogenicity analysis and a supporting analysis may be performed using the evaluable population according to the criteria outlined in [Section 3.5.4](#).

If all 8 co-primary endpoints result in a conclusion of non-inferiority then overall non-inferiority of Seqirus QIV compared to the US-licensed comparator QIV will be concluded.

This assessment will be conducted overall (the primary endpoint).

In mathematical notation the statistical hypotheses to be tested for the primary immunogenicity analysis corresponds to:

H0:  $R_i > 1.5$ , for any strain

Ha:  $R_i \leq 1.5$ , for all strain

and

H0:  $D_i > 10$ , for any strain

Ha:  $D_i \leq 10$ , for all strain

where  $R_i$  is any of the 4 strain-specific post immunogenicity dose GMT ratios:

- (US-licensed comparator QIV) / (Seqirus QIV) for B/Yamagata strain
- (US-licensed comparator QIV) / (Seqirus QIV) for B/Victoria strain
- (US-licensed comparator QIV) / (Seqirus QIV) for A/H1N1 strain
- (US-licensed comparator QIV) / (Seqirus QIV) for A/H3N2 strain

and  $D_i$  is the 4 strain-specific post-dose SCR difference, namely

- (US-licensed comparator QIV) - (Seqirus QIV) for B/Yamagata strain
- (US-licensed comparator QIV) - (Seqirus QIV) for B/Victoria strain
- (US-licensed comparator QIV) - (Seqirus QIV) for A/H1N1 strain
- (US-licensed comparator QIV) - (Seqirus QIV) for A/H3N2 strain

No adjustment will be made for multiple comparisons.

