1.3 STUDY OVERVIEW

The present study is a phase 3, randomized, multicenter, observer-blinded study to evaluate the immunogenicity and safety of Seqirus QIV in comparison with a US-licensed 2016-2017 quadrivalent influenza vaccine (Comparator QIV) in children 6 months through 59 months of age. Seqirus QIV is intended for active immunization against influenza disease caused by influenza virus subtypes A and types B present in the vaccine. In the US, routine annual influenza vaccination of all persons 6 months of age and older continues to be recommended [[Centers for Disease Control and Prevention, 2013](#)].

The study will be conducted during the 2016-2017 Northern Hemisphere influenza immunization season in male and female children 6 months through 59 months of age. Subjects will be randomized to either treatment group in a 3:1 ratio (Seqirus QIV: Comparator QIV). The randomization will be stratified by age stratum into two study cohorts (Cohort A: 6 months through 35 months of age, and Cohort B: 36 months through 59 months of age). Age stratification will employ a quota to ensure that no more than 60% of the total sample subjects are represented in each age stratum. An interactive response technology (IRT) system will be used for subject randomization.

Subjects will receive either one or two doses of Study Vaccine (Seqirus QIV or Comparator QIV) as clinically indicated, depending on their previous history of influenza virus vaccination, in accordance with influenza vaccination dose recommendations of the US Advisory Committee on Immunization Practices (ACIP) for Prevention and Control of Seasonal Influenza with Vaccines. See [Section 3](#) for more information on the ACIP recommendations, dose and dosing regimen.

Immunogenicity assessment will occur prevaccination, and approximately 29 days after the last study vaccination dose by serological assessment with the hemagglutination inhibition (HI) assay. Safety monitoring will include solicited local reactions and systemic adverse events (reactogenicity) for 7 days following each study vaccination dose; unsolicited adverse events for at least 28 days following the last study vaccination dose; and cellulitis-like reactions for at least 28 days following the last study vaccination dose. Serious adverse events monitoring will continue for 180 days following the last study vaccination dose.

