### 3.9 Sample Size

Seqirus QIV will be tested against a US-licensed comparator QIV. The treatment randomization ratio is 3:1 (Seqirus QIV: Comparator QIV).

This study is designed to achieve at least 80% power to demonstrate noninferiority for all of the 8 co-primary endpoints, seroconversion rates for 4 strains, GMT for 4 strains using a one-sided alpha of 0.025 for each comparison. No adjustment for multiple endpoints was made. For comparisons of SCR a noninferiority margin of 10% (Comparator QIV-Seqirus QIV) will be employed. It is assumed that the SCR for all strains for QIV is 50% and that there is no difference between Seqirus QIV and Comparator QIV.

For comparison of GMT ratio a noninferiority margin of 1.5 (Comparator QIV/ Seqirus QIV, equivalent to a difference on the log scale of 0.405465108) will be employed. It is assumed that there is no difference between Seqirus QIV and Comparator QIV (ie, a ratio of 1, difference on the log scale of 0) and that the standard deviation of log (titer) is 1.4.

Under these assumptions and with n evaluable = 1500 in the Seqirus QIV group and 500 in the Comparator QIV the power for 4 GMT ratio endpoints is 99.95% and the power for 4 SCR endpoints is 89.70%. The overall global power of the 8 endpoints is then  $89.7\% \times 99.95\% = 89.66\%$ .

This provides a total N evaluable = 2000 (with 10% dropouts N=2222).

Sample size calculations were performed using SAS v9.3 and PASS v12.0.02.

[Table 3.9-1](#) summarises the list of all primary endpoints with strains, the planned noninferiority margin and underlying assumptions used for the sample size computations.

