**Table 3.9-1 Summary of Assumptions Used for Sample Size Calculations**

	H1N1	H3N2	B strains
Test significance level, alpha (1-sided)	2.50%	2.50%	2.50%
Noninferiority Margin for the SCR comparison (%)	10	10	10
Assumed true SCR	50%	50%	50%
Power for SCR comparison tests for each strain (%)	97.32%	97.32%	97.32%
Global Power for 4 SCR Endpoints	89.70%		
Noninferiority Margin for the GMT ratio	1.5	1.5	1.5
Common Standard Deviation of $\log_e(\text{titre})$	1.4	1.4	1.4
Power for GMT ratio tests for each strain (%)	99.99%	99.99%	99.99%
Global Power for 4 GMT ratio Endpoints	99.95%		
Global Power for 8 Co-primary Endpoints	89.66%		

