## 4.9 Adjustment for Covariates

The complete set of covariates that will be used to calculate the adjusted GMT ratio will include treatment group (2 treatments), pre-vaccination mean GMT titer (value), age strata (2 categories, 6 through 35 months or 36 through 59 months), gender (male or female), influenza vaccination received prior year (Yes or No), number of doses (1 or 2) and investigator site (site identifier) as described in [Section 4.7.2](#).

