#### 5.3.2 Immunogenicity

Table 14.2.1.1	Primary Analysis of Geometric Mean Titer (GMT)
Table 14.2.1.2	Primary Analysis of Geometric Mean Titer (GMT) (Evaluable Population)
Table 14.2.2.1	Primary Analysis of Seroconversion Rate (SCR)
Table 14.2.2.2	Primary Analysis of Seroconversion Rate (SCR) (Evaluable Population)
Table 14.2.3.1	HI Titer Pre-Vaccination (Day 1) and Post-Vaccination (Study Exit Visit)
Table 14.2.3.2	HI Titer Pre-Vaccination (Day 1) and Post-Vaccination (Study exit): By Age Strata
Table 14.2.3.3	HI Titer Pre-Vaccination (Day 1) and Post-Vaccination (Study exit): By Gender
Table 14.2.3.4	HI Titer Pre-Vaccination (Day 1) and Post-Vaccination (Study exit): By Race
Table 14.2.3.5	HI Titer Pre-Vaccination (Day 1) and Post-Vaccination (Study exit): By Ethnicity
Table 14.2.4.1	HI Titer Fold Increase
Table 14.2.4.2	HI Titer Fold Increase: By Age Strata
Table 14.2.4.3	HI Titer Fold Increase: By Gender
Table 14.2.4.4	HI Titer Fold Increase: By Race
Table 14.2.4.5	HI Titer Fold Increase: By Ethnicity
Table 14.2.5.1	Seroconversion Rate (SCR)
Table 14.2.5.2	Seroconversion Rate (SCR): by Age Strata

Table 14.2.5.3	Seroconversion Rate (SCR): by Gender
Table 14.2.5.4	Seroconversion Rate (SCR): by Race
Table 14.2.5.5	Seroconversion Rate (SCR): by Ethnicity
Table 14.2.6	Influenza-Like Illness
Table 14.2.7.1	Antipyretics
Table 14.2.7.2	Antipyretics: by Age Strata

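### As written, the four co-primary seroconversion intervals ignore the age stratification used in randomisation; if seroconversion differs by age, they are somewhat wider than needed

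*SAP*

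**What the plan says.** Protocol Section 1.3 states: "The randomization will be stratified by age stratum into two study cohorts". SAP Section 3.7 gives 3:1 allocation and caps either age stratum at 60% of the sample. SAP Section 3.2 gives the two strata different dose volumes.

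SAP Section 4.7.2 handles the two co-primary families differently:

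- **GMT ratio.** A linear model on log titer includes age stratum, among other covariates, and an age-by-vaccine term that is dropped if not significant. The adjusted ratio decides noninferiority.
- **SCR difference.** The comparator rate minus the Seqirus rate, with a 10-point margin on the upper 95% limit. The only statement on method is: "The 95% CI will be computed based on the binomial distribution".

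The same section says of the level of the test: "This assessment will be conducted overall (the primary endpoint". SAP Section 4.9 introduces its covariate list as "The complete set of covariates that will be used to calculate the adjusted GMT ratio" and does not extend it to SCR. SAP Section 3.9 uses one rate for planning: "It is assumed that the SCR for all strains for QIV is 50" (percent), with no split by age. SCR by age appears only as a secondary summary, in the table titled "Seroconversion Rate (SCR): by Age Strata" (Section 5.3.2).

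The code in SAP Section 4.14 is redacted, so the actual interval cannot be seen. The notes left visible there refer to two-by-two tables, which fits an unstratified interval but does not prove one.

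**The concern.** When randomisation is stratified by a factor related to the outcome, the arms are balanced on that factor by design. An interval built from the two overall proportions uses the total binomial variance p(1−p), which includes variation between strata. That variation does not contribute to the error of the treatment difference, so the interval is wider than it has to be.

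Any such loss would fall on the SCR tests, which limit power in this plan: SAP Table 3.9-1 gives 89.70% for "Global Power for 4 SCR Endpoints" and 99.95% for the four GMT tests, and all eight must succeed. The randomisation factor is used for the family with power to spare and, on the text, not for the other. The SAP gives no reason.

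**Working it through.** **Inputs.** From SAP Section 3.9: 500 comparator and 1500 Seqirus evaluable subjects, SCR 50% in both arms, margin 0.10, and testing "using a one-sided alpha of 0.025 for each comparison". From Section 3.7: each stratum is 40 to 60% of the sample. Assumed here, because the documents give no figure: the gap in SCR between age strata, taken as equal in all four strains. Strains are multiplied as independent, as in the plan.

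**Reproducing the plan.** Write k = 1/500 + 1/1500 = 0.002667.

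- SE = √(0.25 × k) = 0.02582. The Farrington–Manning null rates are 0.4746 and 0.5746, with null SE 0.02559. Power = Φ((0.10 − 1.96 × 0.02559)/0.02582) = 97.32% per strain, and to the fourth power 89.70%. Both match Table 3.9-1 exactly, so the planning calculation is a single unstratified comparison.
- The unpooled Wald version gives Φ(0.10/0.02582 − 1.96) = 97.21% and 89.31%. It is used below because it is simple to stratify, and it stands in for the unspecified binomial interval.
- GMT check: Φ(ln 1.5/(1.4 × √k) − 1.96) = 99.99%, and to the fourth power 99.95%, as stated.

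**Crude against stratified.** With 3:1 allocation within strata and mean SCR 50%:

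- crude SE = √(0.25 × k);
- stratified SE = √(v × k), where v is the stratum-weighted mean of p(1−p);
- crude power per strain = Φ((0.10 − 1.96 × SE_crude)/SE_strat), because the estimate truly varies with the stratified SE;
- stratified power per strain = Φ(0.10/SE_strat − 1.96);
- crude one-sided error at the margin = 1 − Φ(1.96 × SE_crude/SE_strat).

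Example, 20-point gap with equal strata (40% and 60%): v = 0.24 and SE_strat = √(0.24 × 0.002667) = 0.02530. Crude power is Φ((0.10 − 0.0506)/0.02530) = 97.46%, or 90.2% for four strains. Stratified power is Φ(3.953 − 1.96) = 97.69%, or 91.1%.

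| Age gap (points) | CI half-width, crude vs stratified (points) | Crude wider by | Four-strain power, crude vs stratified | Crude error at margin |
|---|---|---|---|---|
| 0 | 5.06 vs 5.06 | 0% | 89.3 vs 89.3% | 2.5% |
| 10 | 5.06 vs 5.04 | 0.5% | 89.5 vs 89.8% | 2.4% |
| 20 | 5.06 vs 4.96 | 2.1% | 90.2 vs 91.1% | 2.3% |
| 30 | 5.06 vs 4.83 | 4.8% | 91.3 vs 93.0% | 2.0% |
| 40 | 5.06 vs 4.64 | 9.1% | 92.8 vs 95.4% | 1.6% |

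**Sensitivity.**

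- With a 60/40 split the same formulas give 90.2 vs 91.0% at 20 points and 91.2 vs 92.9% at 30.
- With the gap in one strain only, using 97.21% for each of the other three: at 20 points 0.9721³ × 0.9746 = 89.5% vs 0.9721³ × 0.9769 = 89.7%; at 40 points 90.2 vs 90.8%.

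**Simulation check** (200,000 trials per setting, Wald crude against Mantel–Haenszel-weighted limits, fixed 3:1 within equal strata). Crude error at the margin for gaps of 0, 10, 20, 30 and 40 points was 2.52, 2.43, 2.31, 2.01 and 1.65%. Stratified error stayed between 2.4 and 2.6%.

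**What is estimated.** With 3:1 in each stratum the Mantel–Haenszel weight is (¾N × ¼N)/N = (3/16)N, proportional to stratum size N. The weighted difference is therefore the overall difference that the plan tests.

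**The case against.** The strongest reply is that nothing here is an error. Protocol and SAP agree on a plain difference in rates assessed overall, and that analysis matches the sample-size calculation exactly. Under the plan's single 50% rate the gain is zero. All of the benefit comes from age gaps that the documents do not supply, and crude power itself rises with the gap, so the planned method never falls below its no-gap power. A conservative interval is defensible in a noninferiority trial, and SCR by age will be tabulated anyway. All of this stands, and it keeps the point at the level of an optional improvement.

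Three narrower points also stand:

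- Stratifying SCR by age would not make the two families identical, because the GMT model has several further covariates. It would only bring the randomisation factor into both.
- If the redacted method is an exact interval, moving to a stratified asymptotic one changes two things at once. The figures above measure only the stratification.
- The larger gains need gaps of 30 to 40 points in every strain.

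None of this gives a reason to leave the randomised factor out of the SCR analysis. The 50% rate is a planning assumption. By stratifying on age and adjusting the GMT for it, the plan itself treats age as possibly prognostic.

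**Conclusion.** The point holds, as a matter of efficiency. On the text, the SCR co-primaries are analysed without the age stratification used in randomisation. If SCR differs by age, the interval is wider than needed: by 0.5% at a 10-point gap, about 2% at 20, 5% at 30 and 9% at 40. The corresponding gain in four-strain power from stratifying is 0.3, 0.9, 1.7 and 2.6 points; with no gap it is nil. The crude interval is conservative, so validity is not in question, and power exceeds the 80% target either way.

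This rests on assumed age gaps common to all four strains, independent strains, 3:1 allocation holding within strata among analysed subjects, a Wald interval in place of the unstated one, and a reading of the SAP text without its code.

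**What to change.** State in SAP Section 4.7.2 that, for each strain, the primary SCR difference and its two-sided 95% CI are stratified by randomised age stratum, and name the method: stratified Miettinen–Nurminen or a Mantel–Haenszel risk difference. Keep the crude difference as supportive, as the plan already does for the unadjusted GMT ratio. Naming the method also settles what a binomial interval for a difference means here. The margin and hypotheses stay as they are.

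The cost is a sentence in Section 4.7.2, an entry in Section 4.13 because the analysis then differs from the protocol's plain difference, and a stratified interval in the code. No new data are needed. The change must be made before unblinding. If SCR proves equal in the two strata, the result is essentially unchanged.

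If the sponsor prefers the unstratified interval as primary, the SAP should say so and add the stratified one as a sensitivity analysis.
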